14. CCI
15. This survey should also be assessed in the last visit of screening failures and withdrawals.
16. The weight obtained at Screening Visit 2 will be used to calculate the viral vector dose.
17. To be performed if applicable based on results from previous visit.
18. CCI
19. This assessment should be performed only if a sleep problem has been identified during the initial evaluation at the Screening Visit 1 or the medical history suggests there is a problem affecting child's sleep.

2. LIST OF ABBREVIATIONS

'suspected' SARs	'suspected' serious adverse reactions
°C	degrees Celsius
AAV9	associated virus serotype 9
CCI	
ACDP	Advisory Committee on Dangerous Pathogens
AE	adverse event
ALT	alanine transaminase
AR	ADVERSE REACTION
AST	Aspartate aminotransferase
BBB	blood-brain barrier
BUN	Blood urea nitrogen
CBC	Complete blood cell count
CFR	Code of Federal Regulations
CNS	central nervous system
CRF	Case Report Forms
CRO	Contract Research Organization
CSF	Cerebral spinal fluid
CSHQ	Children's Sleep Habits Questionnaire
CTCAE	Common Terminology Criteria for Adverse Events v4.03
DNA	deoxyribonucleic acid
DQ	Development Quotient
DSMB	Data Safety Monitoring Board
DSUR	Development safety update report
EC	European Commission
ECG	electrocardiogram
ECHO	echocardiogram
EDC	electronic data capture
EEG	Electroencephalogram
ELISA	enzyme-linked immunosorbent assay
EMA	European Medicines Agency
ERA	Environmental Risk Assessment
ERT	enzyme replacement therapy
EU	European Union
EudraCT	European Union Drug Regulating Authorities Clinical Trials

F	bioavailability
FCI	Fluid-Crystalized Index
g	gram
GAG	glycosaminoglycan
GCP	Good Clinical Practice
GGT	gamma-glutamyl transferase
GLP	Good Laboratory Practice
GMO	genetically modified organism
hSGSH	human N-sulfoglucosamine sulfohydrolase
IB	Investigator's brochure
ICF	informed consent form
ICH	International Council for Harmonisation of Technical Requirements for Pharmaceuticals for Human Use
IND	Investigational New Drug (application)
INR	international normalized ratio
IRB	Institutional Review Board
IV	intravenous
kg	kilogram
L	liter/litre(s)
LP	Lumbar puncture
m	meter
min	minute(s)
mL	milliliter(s)
MPS	Mucopolysaccharidosis
MRI	magnetic resonance imaging
NCH	Nationwide Children's Hospital
NOAEL	no-observable-adverse-effect-level
CCI	
PedsQL	Pediatric Quality of Life Inventory™
PICFs	Patient Informed Consent Forms
PSI-4	Parenting Stress Index, 4th Edition
PT	prothrombin time
PTT	partial thromboplastin time
RH	relative humidity
RSI	Reference Safety Information
SAE	serious adverse event
SAP	Statistical Analysis Plan

SAR	SERIOUS ADVERSE REACTION
CCI	
serum/plasma GGT	serum/plasma gamma-glutamyl transpeptidase
SGSH	sulfoglucosamine sulfohydrolase
SMP	Safety Management Plan
SUSAR	SUSPECTED UNEXPECTED SERIOUS ADVERSE REACTION
Ultragenyx	Ultragenyx Pharmaceutical Inc.
USA	United States of America
UV	ultraviolet
WBC	White blood cell
WHO	World Health Organisation
WMA	World Medical Association

3. INTRODUCTION

3.1. Background

MPS IIIA is a devastating lysosomal storage disease, caused by a single gene defect (Neufeld and Cantz, 1971; Neufeld and Muezner, 2014; Weber et al., 1999). Somatic manifestations of MPS IIIA occur in all patients and can vary compared to other MPS disorders. Infants with MPS IIIA may demonstrate normal development at birth. However, the disease is relentlessly progressive, with deterioration of social and adaptive abilities, neurocognitive decline, and premature death. It can be divided into three phases (Wijburg et al., 2013). In the first phase, after 1-2 years of normal development, developmental delay (speech/language delays) and somatic changes (mild coarsening of facial features, frequent otitis media and hearing loss, hepatomegaly, mild dysostosis multiplex) become apparent between ages 1 and 4 years. In the second phase, which typically presents around ages 3-4 years, neurological manifestations become apparent, including severe behavioral problems, regression of skills and progressive mental deterioration. In the final phase, behavioral problems slowly disappear but cognitive decline progresses to a vegetative state with spasticity, seizures and swallowing problems. In MPS IIIA, approximately 70% of children die from complications of the disease prior to reaching their 18th birthday (USA MPS Society and Greenwood labs, unpublished data available on request).

Quite importantly, there is no treatment currently available for the disease (de Ruijter et al., 2011). AAV-mediated gene transfer to restore SGSH activity has emerged as a therapeutic strategy with great potential for MPS IIIA patients.

3.2. Nonclinical Studies

CCI

CCI [Redacted]

Our ABO-102 gene transfer findings are well positioned to move forward to test in a clinical gene transfer trial for patients with MPSIIIA. To date, a single IV administration of scAAV9.U1a.hSGSH has been well tolerated in an ongoing clinical study, ABT-001 (NCT02716246).

3.3. Clinical Program

An observational study in MPS IIIA and MPS IIIB patients was conducted at Nationwide Children’s Hospital (NCH) (Columbus, OH) prior to the initiation of the ABO-102 program. This study enrolled 15 participants with MPS IIIA and 10 participants with MPS IIIB (Truxal et al., 2016). CCI [Redacted]

- [Redacted]
- [Redacted]
- [Redacted]
- [Redacted]

[Redacted]

CCI [Redacted]

CCI

This proposed Phase I/II study is designed to assess the safety and clinical response to the restoration of N-sulfoglucosamine sulfohydrolase (SGSH) enzyme activity in the CNS and periphery following intravenous injection of a self-complementary adeno-associated vector (scAAV9) carrying the human SGSH transgene under the control of the U1a promoter. Based on pre-clinical studies, scAAV9 and the U1a promoter will permit the efficient long-term transgene expression and secretion of functional SGSH, with great potential for achieving clinical benefits in treating neurological, as well as somatic disorders, in MPS IIIA patients. The selected dose is based on the preclinical proof of concept data in the animal model as well as clinical safety data from the ongoing Phase I/II dose escalation study, ABT-001, which also utilizes ABO-102 administered by IV in a pediatric population. In the ABT-001 study, three (3) patients have been treated in Cohort 1 (5×10^{12} vg/kg), three (3) in Cohort 2 (1×10^{13} vg/kg) and eight (8) participants have been treated in the highest dose cohort at 3×10^{13} vg/kg with a favorable safety profile and no treatment-related SAEs reported through more than two years of follow-up in Cohort 1, and Cohort 2 and two years in several participants in Cohort 3.

The intravenous route of administration was selected based on nonclinical studies, and from the clinical perspective brings advantages based on the minimal participant intervention, avoiding safety complications associated with other administration routes (i.e., intrathecal, intracerebroventricular or intraparenchymal injections).

Several gene therapy studies using other transgenes and similar vectors have been conducted without significant adverse events. Clinical studies to date suggest that an immune response will be generated to AAV capsid proteins, but whether an immune response will develop against SGSH remains to be determined. Because the immune system of participants in this study will be exposed to two antigens upon infusion of the gene therapy vector, the AAV9 capsid (a foreign antigen) and the newly synthesized SGSH (a “self-antigen”), humoral and cellular immune responses against both antigens will be monitored.

Following transduction, CD8 T cells may be induced (or memory CD8 T cells be reactivated in participants exposed previously to AAV9) to eliminate transduced cells that express AAV protein-derived epitopes. Results from several clinical trials suggest that immunosuppression, for example with corticosteroids, may be necessary to control the development of a cellular immune response and achieve sustained expression of the enzyme. In the proposed clinical trial, participants will be treated with a short course of prednisolone (1 mg/kg/day from one day prior to the gene transfer to Day 60, with tapering over the ensuing 4-6 weeks).

4. STUDY DESIGN

This Phase I/II clinical trial is an open-label, single dose study of recombinant, self-complementary AAV9 carrying the human N-sulfoglucosamine sulfohydrolase (hSGSH) gene under the control of the U1a promoter, scAAV9.U1a.hSGSH, also known as ABO-102, delivered one time intravenously to MPS IIIA participants.

4.1. Study Population

The target population includes MPS IIIA participants with a DQ lower than 60 in middle and advanced phases of the disease that would not be eligible for the clinical trial ABT-001.

To ensure that both the middle phase and advanced phase of the disease are adequately represented in the study, a similar number of participants with a cognitive age equivalent of above 18 months (middle) and below 18 months (advanced), as assessed by the Bayley Scales of Infant and Toddler Development, will be enrolled.

Although highly unlikely due to the natural evolution of the disease, the clinical trial may potentially include female adolescents that would represent women of childbearing potential in a normal population, as defined in the Clinical Trial Facilitation Group document (HMA, 2014) (Buhrman et al., 2014) for clarification of effective contraception titled Recommendations Related to Contraception and Pregnancy Testing in Clinical Trials. MPS III participants with a severe phenotype in the middle and advanced phases of the disease would present with a very advanced cognitive decline. This means that the female adolescents with MPS III fitting these characteristics do not have sexual relationships and so, are highly unlikely to be in the position to get pregnant. There are no references of any progeny from MPS III patients, so the sponsor considers there is no need to use any additional contraception measures other than the “*de facto*” sexual abstinence. This should be a reliable contraceptive method during the entire period of risk associated with the study that represents the usual lifestyle of the participant. For safety reasons, pregnancy test will be performed on screening, infusion and all MRI/LP study visits; and pregnancy forms will be developed as part of the Safety Management Plan.

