PT/INR/PTT	X		X		X		X	X	X				X					X	X	X	X
Creatinine/BUN	X		X		X		X	X	X				X					X	X	X	X
AST/ALT	X		X		X		X	X	X	X	X	X	X	X	X	X	X	X	X	X	X
Serum/plasma GGT	X		X		X		X	X	X	X	X	X	X	X	X	X	X	X	X	X	X
Alkaline phosphatase	X		X		X		X	X	X				X					X	X	X	X
Alpha-fetoprotein		X											X					X	X	X	X
Amylase	X		X		X		X	X	X	X ¹⁰	X ¹⁰	X ¹⁰	X ¹⁰	X ¹⁰	X ¹⁰	X ¹⁰	X ¹⁰	X ¹⁰	X ¹⁰	X ¹⁰	X ¹⁰
Serum/plasma total bilirubin	X		X		X		X	X	X				X					X	X	X	X
Random glucose	X		X		X		X	X	X				X					X	X	X	X
Troponin	X		X		X		X	X	X		X		X					X	X	X	X
Plasma and leukocyte SGSH enzyme activity levels	X	X					X	X	X		X		X					X	X	X	X

STUDY TIMELINE OF EVENTS																					
Study Interval	Screening		Pre Infusion Visit	Hospital Admission/ Vector Injection (Inpatient)	Inpatient	Follow-Up (Outpatient)															
	Visit #	Visit 1				Visit 2	Visit 3		Visit 4	Visit 5	Visit 6	Labs	Visit 7	Labs	Visit 8	Labs	Labs	Labs	Visit 9	Visit 10	Visit 11
Study Procedures	Day -45 through -1		Day -1	Day 0	Day 1 (24 hrs)	Day 2 (48 hrs)	Day 7 +/- 2 days	Day 14 +/- 2 days	Day 30 +/- 3 days	Day 45 +/- 3 days	Day 60 +/- 7 days	Day 75 +/- 3 days	Day 90 +/- 7 days	2 weeks post steroids +/- 7 days	Day 120 +/- 7 days	Day 150 +/- 7 days	Day 180 +/- 21 days	Month 12 +/- 30 days	Month 18 +/- 30 days	Month 24 +/- 30 days	
Urine GAG/heparan sulfate levels	X				X		X	X	X			X						X	X	X	X
Raw plasma heparan sulfate	X	X			X		X	X	X			X						X	X	X	X
Urinalysis	X				X		X	X	X				X					X	X	X	X
Vector Shedding Samples: Plasma, Urine, Feces, Saliva	X ⁵	X ⁵		X ⁶	X	X	X	X	X		X ⁷		X ⁷					X ⁷	X ⁷	X ⁷	X ⁷
Urine or Serum pregnancy test (if applicable)	X			X															X		X
Gene sequencing to confirm MPS IIIA diagnosis	X ⁸																				
ELISpot	X							X	X	X ¹⁷	X	X ¹⁷	X	X ¹⁷	X ¹⁷			X	X	X	X
ELISA	X						X	X	X		X		X					X	X	X	X
Plasma biobanking		X		X			X	X	X		X		X					X	X	X	X
CCI	X				X		X	X	X		X							X	X	X	X
Serum nAbs	X																	X	X		X
Serology: hepatitis B, C, and HIV		X																			
Sedation/Anesthesia		X		X ³					X									X	X		X
Lumbar puncture		X							X									X	X		X
CSF enzyme activity & heparan sulfate levels		X							X									X	X		X
CSF protein, glucose, cell count and diff		X							X									X	X		X
CCI		X							X									X	X		X
CCI		X							X									X	X		X
CSF Biobanking		X							X									X	X		X
Brain MRI		X																	X		X

STUDY TIMELINE OF EVENTS

Study Interval	Screening		Pre Infusion Visit	Hospital Admission/ Vector Injection (Inpatient)	Inpatient	Follow-Up (Outpatient)														

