	Visit 1	Visit 2				Visit 3		Visit 4	Visit 5	Visit 6	Labs	Visit 7	Labs	Visit 8	Labs	Labs	Labs	Visit 9	Visit 10	Visit 11
Study Procedures	Day -45 through -1	Day -1	Day 0	Day 1 (24 hrs)	Day 2 (48 hrs)	Day 7 +/- 2 days	Day 14 +/- 2 days	Day 30 +/- 3 days	Day 45 +/- 3 days	Day 60 +/- 7 days	Day 75 +/- 3 days	Day 90 +/- 7 days	2 weeks post steroids +/- 7 days	Day 120 +/- 7 days	Day 150 +/- 7 days	Day 180 +/- 21 days	Month 12 +/- 30 days	Month 18 +/- 30 days	Month 24 +/- 30 days	
CCI		X															X		X	
Abdominal MRI		X						X									X	X	X	
CCI		X ¹⁴														X ¹⁸	X ¹⁸		X ¹⁸	
PedsQL Core Generic Scales	X																X	X	X	X
PedsQL Gastrointestinal Symptoms Scales	X																X	X	X	X
CSHQ	X																X ¹⁹	X ¹⁹	X ¹⁹	X ¹⁹
PSI4		X															X	X	X	X
Admit to Hospital			X																	
Study agent administration			X																	
Prophylactic Prednisolone/Prednisolone			X ⁴	X ⁴	X ⁴	X ⁴	X ⁴	X ⁴	X ⁴	X ⁴	X ⁴	X ⁴	X ⁴							
Participant Survey																				X ¹⁵

1. If there are changes to the study, parents will be re-consented at their next visit.
2. Day 0 Vital Signs (Heart rate, respiratory rate, pulse oximetry, temperature, and blood pressure) will be measured before and immediately after the infusion, and at least every five minutes during the infusion, and repeated at 15 minutes post-infusion. VS will be obtained hourly for 4 hours following the injection and then every 4 hours until discharge. Only the following time point will be recorded in EDC: Day 0 pre and post infusion; 1-hour post infusion, 2 hours, 4 hours, 8 hours, 12 hours, 24 hours and 48 hours post infusion.
3. Need for sedation during gene transfer will be decided upon by the PI/designee, in discussion with the anesthesiologist and parent(s) on that day. Appropriate anesthesia (single event per visit) will be provided at Screening, Days 30 and 180, Month 12, and Month 24 with MRI imaging preceding lumbar puncture for safety.
4. Prophylactic prednisolone/prednisone taper begins on Day -1 and is tapered according to AST, ALT, and ELISpot results. Anticipate that most participants will be on prednisolone for 90 to 120 days.
5. Urine, feces and saliva vector shedding samples collected at Screening Visit 1. Plasma vector shedding sample collected at Screening Visit 2. If urine, feces and saliva are not obtained at Screening Visit 1, they will be obtained at Screening Visit 2.

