5.5.2.3. Day 30 (+/- 3 days)

The following evaluations will be conducted at Day 30:

- Medical history
- Adverse events
- Concomitant medications
- Physical examination
- Vital signs (temperature, heart rate, respiratory rate, blood pressure)
- Height and weight
- Abdominal MRI to measure liver and spleen volumes
- Labs will be obtained, including
 - CBC and differential
 - Electrolytes
 - Serum/plasma total protein
 - Albumin
 - PT, PTT, INR
 - Creatinine/BUN
 - AST, ALT, serum/plasma GGT
 - Alkaline phosphatase
 - Amylase
 - Serum/plasma total bilirubin
 - Random glucose
 - Troponin
 - Plasma and leukocyte SGSH enzyme activity levels
 - Plasma heparan sulfate levels
 - Urine GAG and heparan sulfate levels

- Urinalysis
- ELISpots for T-cell responses to AAV9 and SGSH
- ELISA for detection of total antibodies to AAV9 and antibodies to SGSH
- CCI
- Plasma biobanking
- Lumbar puncture (LP) will be performed under sedation/anesthesia
 - CSF analysis
 - SGSH enzyme activity
 - heparan sulfate levels
 - CCI
 - Protein, glucose, cell count and differential
 - CCI
 - CSF biobanking
- Samples for vector shedding (plasma, urine, saliva and feces)

If an elevation in amylase levels is observed after gene transfer and has not returned to baseline values by Day 30, amylase will continue to be analyzed in further visits until levels return to baseline values. Those analyses will include lab collections performed at home if the participant is unable to travel to the hospital.

5.5.2.4. 5.5.2.4 Day 45 (+/- 3 days)

Lab work at Day 45 will be done to evaluate safety. Participants unable to travel to the hospital will have their blood drawn by a contracted home care service.

The labs will evaluate:

- ○ AST, ALT, serum/plasma GGT

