5.5.2.10. Day 180 (+/- 21 days)

The following evaluations will be conducted at Day 180:

- Medical history
- Adverse events

- Concomitant medications
- Physical examination with a head circumference measurement
- Vital signs (temperature, heart rate, respiratory rate, blood pressure)
- Height and weight
- Neurocognitive validity form
- Cognitive function assessment using:
 - Vineland Adaptive Behavior Scale II-Survey form, parental rating of adaptive functioning
 - Mullen Scales of Early Learning, both non-verbal assessments of cognitive function. If children obtain a developmental age older than 60 months with the Mullen, the Kaufman Assessment Battery for Children, Second Edition, will also be used and will replace the Mullen Scales in the next visits
 - Bayley Scales of Infant and Toddler Development – Version III- Cognitive, Language and Motor. If children obtain a developmental age older than 36 months with the Bayley, the Kaufman Assessment Battery for Children, Second Edition, will also be used and will replace the Bayley Scales in the next visits
 - CCI [REDACTED]
 - Parenting Stress Index, 4th Edition (PSI-4) short form
 - Pediatric Quality of Life Inventory (PedsQL™) Core Generic Scales for parents
 - Pediatric Quality of Life Inventory PedsQL™ Gastrointestinal Symptoms Scales for parents
- Modified Children’s Sleep Habits Questionnaire (CSHQ) (This scale will be used if a sleep problem has been identified during the initial evaluation in Screening visit 1 or the medical history suggests there is a problem affecting child’s sleep)
- Parent Global Impression Score
- Clinical Global Impression Improvement Scale
- Parent Symptom Score Questionnaire
- The participant will be CCI [REDACTED] walking a 25-meter distance
- Abdominal MRI to measure liver and spleen volumes
- 45-min EEG
- CCI [REDACTED]
- Echocardiogram
- ECG

- CCI [REDACTED]
- Labs will be performed including
 - CBC and differential
 - Electrolytes
 - Serum/plasma total protein
 - Albumin
 - PT, PTT, INR
 - Creatinine/BUN
 - AST, ALT, serum/plasma GGT
 - Alkaline phosphatase
 - Alpha-fetoprotein
 - Serum/plasma total bilirubin
 - Random glucose
 - Troponin
 - Plasma and leukocyte SGSH enzyme activity levels
 - Plasma heparan sulfate levels
 - CCI [REDACTED]
 - Urine GAG and heparan sulfate levels
 - Urinalysis
 - ELISpots for T-cell responses to AAV9 and SGSH
 - ELISA for detection of total antibodies to AAV9 and antibodies to SGSH
 - CCI [REDACTED]
 - Plasma biobanking

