5.5.2.11. Month 12 (+/- 30 days)

The following evaluations will be conducted at Month 12:

- Medical history
- Adverse events
- Concomitant medications
- Physical examination with a head circumference measurement
- Vital signs (temperature, heart rate, respiratory rate, blood pressure)
- Height and weight
- Neurocognitive validity form
- Cognitive function assessment using:
 - Vineland Adaptive Behavior Scale II-Survey form, parental rating of adaptive functioning
 - Mullen Scales of Early Learning, both non-verbal assessments of cognitive function. If children obtain a developmental age older than 60 months with the Mullen, the Kaufman Assessment Battery for Children, Second Edition, will be used also and will replace the Mullen Scales in the next visits
 - Bayley Scales of Infant and Toddler Development – Version III – Cognitive, Language and Motor. If children obtain a developmental age older than 36 months with the Bayley, the Kaufman Assessment Battery for Children, Second Edition, will be used also and will replace the Bayley Scales in the next visits
 - **CCI** [REDACTED]
 - Parenting Stress Index, 4th Edition (PSI-4) short form
 - Pediatric Quality of Life Inventory (PedsQL™) Core Generic Scales for parents
 - Pediatric Quality of Life Inventory PedsQL™ Gastrointestinal Symptoms Scales for parents
- Modified Children’s Sleep Habits Questionnaire (CSHQ) (This scale will be used if a sleep problem has been identified during the initial evaluation in Screening visit 1 or the medical history suggest there is a problem affecting child’s sleep)
- Parent Global Impression Score

- Clinical Global Impression Improvement Scale
- Parent Symptom Score Questionnaire
- The participant will be CCI walking a 25-meter distance
- CCI
- Abdominal MRI to measure liver and spleen volumes
- 45-min EEG
- CCI
- Echocardiogram
- ECG
- CCI
- CCI
- Labs will be performed including:
 - CBC and differential
 - Electrolytes
 - Serum/plasma total protein
 - Albumin
 - PT, PTT, INR
 - Creatinine/BUN
 - AST, ALT, serum/plasma GGT
 - Alkaline phosphatase
 - Alpha-fetoprotein
 - Serum/plasma total bilirubin
 - Random glucose
 - Troponin
 - Plasma and leukocyte SGSH enzyme activity levels
 - Plasma heparan sulfate levels
 - CCI
 - Urine GAG and heparan sulfate levels
 - Urinalysis

- ELISpots for T-cell responses to AAV9 and SGSH
- ELISA for detection of total antibodies to AAV9 and antibodies to SGSH
- CCI [REDACTED]
- Urine pregnancy test (if applicable)
- Plasma biobanking

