3 STUDY OVERVIEW

3.1 Study Design

This Phase I/II clinical trial is an open-label, single dose study of recombinant, selfcomplementary Adeno-Associated Viral Vector (AAV9) carrying the human Nsulfoglucosamine sulfohydrolase (hSGSH) gene under the control of the U1a promoter, scAAV9.U1a.hSGSH, also known as ABO-102, delivered one time intravenously to MPS IIIA participants. The target population includes MPSIIIA participants with a Developmental Quotient (DQ) lower than 60 in middle and advanced phases of the disease that would not be eligible for the clinical trial ABT-001. To ensure that both the middle phase and advanced phase of the disease are adequately represented in the study, a similar number of participants with a cognitive age equivalent of above 18 months (middle) and below 18 months (advanced), as assessed by the Bayley Scales of Infant and Toddler Development, will be enrolled.

During the active phase of the protocol, subjects will have 12 clinic visits and 5 labs visit over a two-year period. However, due to the study early termination, there will be at most 10 clinic visits and 5 lab visits over a one-year period. Unscheduled visits may be needed per the discretion of the investigator. Efficacy and safety will be evaluated.

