5.1 Intent-to-Treat Set (ITT)

The ITT Set will include all enrolled subjects who received ABO-102 and have at least one post-baseline efficacy measurement. Efficacy and safety analyses will be conducted based on the ITT Population.

The primary endpoints, secondary endpoints, **CCI** endpoints will be analyzed using the ITT Set. At the time of the study termination, all 5 enrolled subjects were treated and had at least one post-baseline assessment. Therefore, the ITT Population is equivalent to all patients enrolled and will be used to evaluate both safety and efficacy data and for populating listings.

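### Protocol 4.1 requires a pregnancy test at every MRI/LP visit, but the schedule and visit lists leave it out at Days 30 and 180

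*Protocol*

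**What the plan says.** Protocol Section 4.1 explains why no contraception beyond abstinence is required and then sets a safety rule: a "pregnancy test will be performed on screening, infusion and all MRI/LP study visits".

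Footnote 3 of the Schedule of Evaluations identifies the visits at which MRI and lumbar puncture (LP) share one anesthesia event. They are Screening and "Days 30 and 180, Month 12, and Month 24 with MRI imaging preceding lumbar puncture for safety". The visit lists agree. Day 30 (Section 5.5.2.3) has an abdominal MRI, and "Lumbar puncture (LP) will be performed under sedation/anesthesia". Day 180 (Section 5.5.2.10) lists "Abdominal MRI to measure liver and spleen volumes" and also an LP under sedation or anesthesia.

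In the Schedule of Evaluations, the row beginning "Urine or Serum pregnancy test (if applicable" is marked at Screening Visit 1, Day 0, Month 12 and Month 24 only. SAP Table 1 carries the same four marks. The visit lists follow the row. The Month 12 list (Section 5.5.2.11) contains "Urine pregnancy test (if applicable", and the Month 24 list has the same entry. The Day 30 and Day 180 lists have no pregnancy test.

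**The concern.** Section 4.1 and the operational parts of the protocol give different instructions for the same two visits. Sites usually work from the schedule and the visit lists, so a site doing so could omit a check that Section 4.1 requires for safety, at two visits with MRI, LP and anesthesia. Because Section 4.1 asks for no contraception beyond abstinence, testing is the check it relies on for any female participant of childbearing potential.

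There is also a small consequence for reporting. SAP Section 7.5 lists all protocol deviations, including departures from study procedures, and has them classed as major or minor. For an applicable female, the documents do not settle whether an untested Day 30 or Day 180 visit is a deviation.

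**Working it through.** The plan gives no figure to reproduce. The check sets the rule beside the schedule and the visit lists.

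| Visit | MRI and LP? | Test required by 4.1? | Test in schedule row? | Test in visit list? |
|---|---|---|---|---|
| Screening | Yes (Visit 2) | Yes | Yes (Visit 1) | Yes (Visit 1) |
| Day 0 | No (infusion) | Yes | Yes | Yes |
| Day 30 | Yes | Yes | **No** | **No** |
| Day 180 | Yes | Yes | **No** | **No** |
| Month 12 | Yes | Yes | Yes | Yes |
| Month 24 | Yes | Yes | Yes | Yes |

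Three other explanations were considered.

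- **Table layout.** The schedule columns are hard to read in the extracted text. Aligned with the LP row of the same table, the last two pregnancy-test marks fall on Months 12 and 24, and Days 30 and 180 are blank. The four visit lists that contain the test match the four marks.
- **Redaction.** The Day 30 and Day 180 lists contain redacted lines. The test is printed openly wherever else it appears, and its schedule row is not redacted, so concealment at only these two visits is not credible.
- **Meaning of the terms.** The applicability qualifier limits who is tested, not when, and it accompanies the test at Months 12 and 24 as well. Reading MRI as brain MRI only would leave Months 12 and 24, but Section 4.1 covers all MRI/LP visits and footnote 3 counts Days 30 and 180 among them.

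Size of the gap:

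- Planned post-dose MRI/LP visits: Day 30, Day 180, Month 12, Month 24 = 4. Test listed at 2. Missing: 4 − 2 = 2 of 4.
- Under the early termination in SAP Section 3.1 ("there will be at most 10 clinic visits and 5 lab visits over a one-year period"), the visits are Day 30, Day 180 and Month 12 = 3. Test listed at 1. Missing: 3 − 1 = 2 of 3.
- Interval between scheduled tests, Day 0 to Month 12, taking 12 months as 365 days (an assumption): 365 days. With the ±30-day visit window: 365 − 30 = 335 to 365 + 30 = 395 days. With the 30-day month of SAP Section 7.6: 12 × 30 = 360 days, range 330 to 390.
- Tests affected: (0 to 5 applicable subjects) × 2 visits = 0 to 10. At the planned enrollment of 12: (0 to 12) × 2 = 0 to 24.

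**The case against.** The strongest reply is that this is a clerical mismatch with almost no consequence. Section 4.1 is itself operative text, so the requirement to test at Days 30 and 180 exists, and a site reading the whole protocol would find it. The stray wording may be the phrase in Section 4.1: the schedule row and four visit lists agree with each other, and the version 4.0 change summary describes adding the test at Day 0 and Months 12 and 24. Narrowing Section 4.1 would remove the conflict without adding procedures for severely impaired children. Screening and Day 0 tests already cover the single vector exposure, and Section 6.6 requires any pregnancy to be reported within 24 hours and followed to outcome. The range of 0 to 10 tests includes zero, and its upper end needs all 5 subjects to be applicable females who attended both visits.

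Much of this stands. The gap is in the schedule and lists, not in every part of the protocol. The effect is very small, the test-count range says little, and the point concerns internal consistency rather than any endpoint or analysis. None of it removes the conflict between Section 4.1 and the schedule. Reconciling in the other direction is possible, but it would withdraw two safety checks that the protocol says will be done, and the documents give no reason for doing so.

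**Conclusion.** The concern holds. As written, the schedule and visit lists do not carry out the Section 4.1 rule at Days 30 and 180, which is 2 of 4 planned post-dose MRI/LP visits or 2 of 3 under one-year follow-up. The scheduled tests leave an interval of about one year after dosing.

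The importance is low. The protocol itself considers pregnancy highly unlikely in this population, and no efficacy endpoint is affected. Few subjects are involved: "At the time of the study termination, all 5 enrolled subjects were treated". The number of those 5 who were females to whom the test applied, and their attendance at both visits, are not given, so the number of missed tests could be zero. The conclusion rests on reading Days 30 and 180 as MRI/LP visits, which footnote 3 and both visit lists support directly.

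**What to change.** Add the urine pregnancy test, with the same applicability qualifier used at Month 12, to the laboratory lists in Protocol Sections 5.5.2.3 (Day 30) and 5.5.2.10 (Day 180). Mark Day 30 and Day 180 in the pregnancy-test row of the Schedule of Evaluations and of SAP Table 1. All four places then agree with Section 4.1.

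The cost is one urine test at each of two existing visits for any applicable female: at most 5 × 2 = 10 tests for the treated subjects, or 12 × 2 = 24 at planned enrollment. No analysis changes. With the study ended early, the practical value of the correction is limited.
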